### 9.3.2.3 Use of rescue medication due to an absence or loss of clinical benefit

**Table 9-4: Estimands for the secondary efficacy endpoint: absence or loss of clinical benefit - use of rescue medication**

Statistical category	Estimand:		
	Analysis set	Intercurrent event handling strategy	Population-level summary (Analysis):
Secondary	RS	1. Treatment policy strategy: Temporary discontinuation of the IMP will not affect the assessment of the endpoint. 2. Composite strategy: Permanent discontinuation of the IMP due to a reason other than an absence or loss of clinical benefit will not be considered as meeting the endpoint.	The association between the randomized treatment and the use of rescue medication during the Treatment Period will be measured by the rozanolixizumab versus placebo common OR and tested for a conditional (across the strata effects; see Section 6.3) independence using the CMH test. The outcomes will be summarized and analyzed as described in the primary estimand analysis (see Section 9.3.1.1).
Supplementary	RS	As described for the secondary estimand analysis.	The association between the randomized treatment and the use of rescue medication during the Treatment Period will be measured by the difference between

**Table 9-4: Estimands for the secondary efficacy endpoint: absence or loss of clinical benefit - use of rescue medication**

Statistical category	Estimand: Treatment: Randomized rozanolixizumab or placebo in study participants who are concurrently treated with iv or oral steroids. Population: Study participants with LGI1 AIE as specified in the inclusion and exclusion criteria (Section 5.1 and Section 5.2), respectively. Endpoint (Variable): Use of rescue medication due to an absence or loss of clinical benefit during the Treatment Period. Intercurrent events: The study participant: 1. Temporarily discontinued from the IMP 2. Permanently discontinued from the IMP		
	Analysis set	Intercurrent event handling strategy	Population-level summary (Analysis):
			rozanolixizumab and placebo arms in the proportion of study participants reaching the secondary endpoint, controlling for the effect of stratification factors (see Section 6.3). The outcomes will be summarized and analyzed as described in the relevant primary estimand supplementary analysis (see Section 9.3.1.1).

AIE=autoimmune encephalitis; CMH=Cochran-Mantel-Haenszel; FAS=Full Analysis Set; IMP=investigational medicinal product; iv=intravenous; LGI1=leucine-rich glioma inactivated 1; OR=odds ratio; RS=Randomized Set.

### 9.3.2.4 Time to first occurrence of seizure freedom

**Table 9-5: Estimands for the secondary efficacy endpoint: TTFSF**

Statistical category	Estimand:		
	Analysis set	Intercurrent event handling strategy	Population-level summary (Analysis):
Secondary	RS	
 
1. Treatment policy strategy: Temporary discontinuation of the IMP will not affect the assessment of the endpoint.
 
2. While on treatment strategy: For permanent discontinuation of the IMP the participant will be censored on the final day while on the IMP.
 
	
The null hypothesis of no difference between the TTFSF hazard functions for the randomized treatment arms adjusting for the effect of stratification factors (see Section 6.3), will be tested using a stratified log-rank test with the Breslow approach for handling ties. The rozanolixizumab versus placebo hazard ratio estimate based on the stratified log-rank test and its 95% CI will be reported together with the stratified log-rank test p-value. The assumption underlying the utilized statistical methodologies is that any censoring is non-informative, ie, independent from the event of interest. The TTFSF will be presented graphically by treatment arm using a Kaplan-Meier plot, along with median TTFSF estimates reported.

AIE=autoimmune encephalitis; CI=confidence interval; FAS=Full Analysis Set; IMP=investigational medicinal product; iv=intravenous; LGI1=leucine-rich glioma inactivated 1; RS=Randomized Set; TTFSF=time to first occurrence of seizure freedom

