#### **7.1.3 Permanent discontinuation due to absence or loss of clinical benefit**

Study participants **must be permanently discontinued from IMP** if they do not experience a clinical improvement within the first 4 weeks of the Treatment Period (ie, an absence of clinical benefit) or if they experience clinical worsening (ie, a loss of clinical benefit) at any time as defined by any of the following:

1. mRS assessment
  - a. Worsening of 1 point compared with Baseline; or
  - b. Lack of improvement of a severe score (4 or 5) after 4 weeks
2. Worsening of cognitive function: A decrease of  $\geq 8$  points in the total RBANS score compared to Baseline, and per the assessment of the investigator that the study participant has worsened
3. A clinically meaningful recurrence of seizures of a previously experienced type or a new seizure type, either of those requiring a change in therapy (per the assessment of the investigator)
4. Lack of seizure improvement (per the assessment of the investigator)

If study participant permanently discontinues from IMP for any reason, investigators should contact the medical monitor, whenever possible, to discuss the withdrawal of a participant in advance. Study participants who permanently discontinue the IMP should complete the assessments outlined for the EOT/EDisc Visit and enter the 8-week SFU Period. If IMP is permanently discontinued, the requirement for, and selection of, rescue therapy will be made by the investigator.

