**Table 9-1: Estimands for the primary efficacy endpoint**

Statistical category	Estimand:		
	Analysis set	Intercurrent event handling strategy	Population-level summary (Analysis):
Primary	RS	

1. Treatment policy strategy: Temporary discontinuation of the IMP will not affect the assessment of the primary endpoint.

2. Composite strategy: Permanent discontinuation of the IMP will be considered as a failure in meeting the primary endpoint.

	The association between randomized treatment exposure and the primary endpoint will be measured by the rozanolixizumab versus placebo common OR derived from the 2x2 contingency tables corresponding to the stratification factors (see Section 6.3). The null hypothesis, $H_0$ : (true) common OR=1, indicating no effect between the treatment exposure and the primary endpoint, will be tested using a CMH test. The CMH estimate of the common OR will be reported with its 95% CI and the CMH test p-value. The assumptions of the CMH test will be validated (Mantel-Fleiss criterion) and, if appropriate, the exact stratified test of independence alternative will be considered.
Sensitivity	FAS	As described for the primary estimand analysis.	As described above.
Sensitivity	RS	As described for the primary estimand analysis.	Logistic regression model including effect for randomized treatment, conditional on the stratification factors (see Section 6.3), will be used to test the primary efficacy hypothesis. The resulting rozanolixizumab versus placebo common OR estimate with its 95% CI and the treatment factor p-value from the model will be reported. As a part of the analysis, the model will be extended to include an additional binary covariate to

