### 9.3.2 Secondary efficacy analysis

The secondary study objectives are the assessment of the efficacy of rozanolixizumab as measured by a change from Baseline in cognitive function (assessed using the RBANS; Section 9.3.2.1), change in overall disability function (assessed using the mRS scores; Section 9.3.2.2), use of rescue medication due to an absence or loss of clinical benefit (Section 9.3.2.3), and time to first occurrence of seizure freedom (Section 9.3.2.4).

A fallback hierarchical testing procedure will be implemented to control the overall type I familywise error rate at 0.05 over the primary endpoint and the 4 alpha-controlled secondary endpoints. In the event that the null hypothesis relating to the primary endpoint is rejected at 2-

sided 5% significance, then the secondary endpoints will be tested in the following order with the corresponding allocations of alpha, implementing the fallback method of multiplicity control:

1. Change from Baseline in RBANS total scale index score at the end of the Treatment Period (Week 25; Alpha=0.046) (Section 9.3.2.1)
2. Proportion of participants with a favorable outcome in mRS at the end of the Treatment Period (Week 25; Alpha=0.002) (Section 9.3.2.2)
3. Use of rescue medication due to an absence or loss of clinical benefit during the Treatment Period (Alpha=0.001) (Section 9.3.2.3)
4. Time to first occurrence of seizure freedom (Alpha=0.001) (Section 9.3.2.4)

For each of the listed endpoints, the hypothesis test will only be considered inferential if the endpoint meets statistical significance at its individual allocated level, or in accordance with the fallback methodology where the preceding endpoints are statistically significant thus allowing the alpha allocated to these preceding endpoints to be carried forward to subsequent endpoints. This carryforward of the alpha level is automatically halted at the point that an endpoint in the defined sequence is not statistically significant at the testing level assigned by the fallback rule.

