### 9.3.3 Exploratory efficacy analyses

#### 9.3.3.1 Time to seizure freedom maintenance (TTSFM)

The time to seizure freedom maintenance (TTSFM) defined by the number of days after randomization to the first day of the 28 consecutive days without seizures, ‘maintained until the end of the Treatment Period (Week 25)’.

This analysis and summaries of the time to seizure freedom maintenance endpoint will be performed on the RS utilizing the methodology as described for the TTFSF endpoint (see

Section 9.3.2.4). The participants who do not reach the described endpoint criteria will be censored at the last follow-up timepoint.

In addition, as a further exploratory endpoint, this analysis and summaries will be repeated for only the subgroup of participants who achieved the seizure freedom endpoint criteria.

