**Table 9-6: Study operating characteristics**

Sample size	PBO arm SF proportion (%) at the end of Treatment Period	R arm SF proportion (%) at the end of Treatment Period	Power CMH a (%)	Power logistic b (%)	Target R-PBO SF proportion difference (%)	Probability c (%)		
						Scenario A	Scenario B	Scenario C
60	40	70	54.6	63.2	30	45.7	20.6	33.8
					40	17.3	49.1	33.6
					50	3.7	62.8	33.5
60	40	80	84.5	86.0	30	76.3	14.1	9.6
					40	45.2	45.3	9.5
					50	16.1	74.7	9.2
60	40	90	98.3	95.4	30	95.6	3.8	0.6
					40	79.1	20.0	0.9
					50	44.5	54.8	0.7

CMH= Cochran-Mantel-Haenszel; PBO=placebo; R=rozanolixizumab; SF=seizure freedom

a Power to detect a statistical difference at a 2-sided 5% significance level based on the CMH test with continuity correction (Wittes and Wallenstein, 1987).

b Power to detect a statistical difference at a 2-sided 5% significance level from a standard logistic regression model adjusting for treatment group (Demidenko, 2007).

c Derived from the Fisch et al (2015) decision framework based on dual criteria: Significance – high confidence (0.975) that the effect of the investigational drug, relative to placebo, is greater than zero; Relevance - moderate confidence (0.5) that the drug effect, relative to placebo, is larger than the target difference. Possible scenarios: A – both criteria hold as an evidence of sufficiently high effect; B – inconclusive as only one criterion holds, suggesting a marginal effect (Significance only) or too much variability to make a clear decision (Relevance only); C – neither of the criteria holds. The probability of each scenario calculated from S=10,000 simulated study outcomes for a given sample size and seizure freedom proportions combination.

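### Protocol Table 9-5 censors TTFSF on the last IMP day and assumes non-informative censoring, although Section 7.1.3 requires IMP to be stopped for lack of seizure improvement

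*Protocol*

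**What the plan says.** - **TTFSF rule.** Protocol Table 9-5 labels its handling of permanent discontinuation as while on treatment: "For permanent discontinuation of the IMP the participant will be censored on the final day while on the IMP". No reason for stopping is distinguished.
- **TTFSF assumption.** The stratified log-rank test, hazard ratio and Kaplan-Meier plot rest on the premise that "any censoring is non-informative, ie, independent from the event of interest". The table lists no sensitivity analysis.
- **Stopping rule.** Protocol 7.1.3 requires permanent IMP discontinuation on several grounds, including "Lack of seizure improvement (per the assessment of the investigator", a seizure recurrence that needs a change in therapy, and mRS or RBANS worsening. Participants who need rescue also leave blinded treatment (6.5.3).
- **Primary endpoint.** Table 9-1 handles the same event differently: "Composite strategy: Permanent discontinuation of the IMP will be considered as a failure in meeting the primary endpoint".
- **TTSFM (9.3.3.1).** It borrows the TTFSF methods but has its own text: "The participants who do not reach the described endpoint criteria will be censored at the last follow-up timepoint".
- **SAP Amendment 1.** With 12 participants, secondary endpoints are summarized and not tested (5.4), and the fallback procedure is dropped (5.1.1.7). TTFSF is summarized as a continuous variable and listed (5.4.4). TTSFM is removed (6.8.1).

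**The concern.** TTFSF is a time-to-success endpoint. A participant taken off IMP because seizures have not improved has a known on-treatment result: no 28-day run. Censoring on the last IMP day replaces that result with the assumption that the participant had the same future chance of success as those still on treatment. The stopping rule makes that assumption false by design. The rule also does not fit its label, because it targets what would have happened had treatment continued, not what happened while on treatment.

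At stake in the protocol plan are the success curve, the median, the hazard ratio and the power of one of the four alpha-controlled secondary endpoints. Table 9-1 counts the same participants as failures, so two seizure-freedom endpoints would treat them in opposite ways.

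**Working it through.** **1. The plan's own figure.** Table 9-6 gives power for the primary endpoint only: "Power to detect a statistical difference at a 2-sided 5% significance level based on the CMH test with continuity correction". With 30 per arm and 40% on placebo, the continuity-corrected calculation gives 54.8%, 84.8% and 98.4% for 70%, 80% and 90% on drug (stated: 54.6, 84.5, 98.3). The Wald logistic calculation gives 63.2%, 86.0% and 95.4%, as stated. The documents give no power, event count or hazard ratio for TTFSF.

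**2. Inputs.** From the protocol: 34 per arm; 40% v 70% or 80% reaching seizure freedom; a 168-day Treatment Period, so the last day on which a 28-day run can start is 168 − 28 + 1 = 141. Section 9.8 cites a 28-day median time to freedom from faciobrachial dystonic seizures in an outside cohort.

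Assumed: onset is exponential with that median, truncated at Day 141; failures never reach freedom on study; a fraction f of failures is stopped, either early (Days 28–56) or spread (Days 28–140).

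**3. Mechanism.** Let p be the proportion who achieve freedom, F the onset distribution among them, and H the distribution of stop days. The hazard that Table 9-5 estimates is

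p·F′(t) ÷ [p(1 − F(t)) + (1 − p)(1 − f·H(t))].

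If stopped failures stay at risk, the f·H(t) term drops out and the denominator is larger. Example at Day 56, f = 50%, early stops:

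- F(56) = 0.75 ÷ (1 − 2^(−141/28)) = 0.774, so 22.6% of achievers are still to come.
- Placebo (13.6 achievers, 20.4 failures): at risk 3.1 + 20.4 = 23.5 if kept, 3.1 + 10.2 = 13.3 if censored. Hazard inflated by 23.5/13.3 = 1.77.
- Drug at 80% (27.2 achievers, 6.8 failures): 6.2 + 6.8 = 13.0 v 6.2 + 3.4 = 9.6. Hazard inflated by 1.36.
- From then on, the hazard ratio is multiplied by 1.36/1.77 = 0.77.

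**4. Simulation.** 1,500 trials per row, unstratified log-rank, two-sided 5%, Monte Carlo error about 0.7 to 1.3 points. Each cell shows Table 9-5 censoring v kept at risk to Day 168.

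| Placebo v drug | Failures stopped | Power, % | Hazard ratio | KM success, placebo | KM success, drug |
|---|---|---|---|---|---|
| 40 v 80 | 10%, spread | 90.8 v 91.1 | 2.94 v 2.96 | 0.41 v 0.40 | 0.81 v 0.80 |
| 40 v 80 | 50%, spread | 90.1 v 91.7 | 2.86 v 2.95 | 0.44 v 0.40 | 0.84 v 0.80 |
| 40 v 80 | 50%, early | 87.5 v 91.9 | 2.71 v 2.96 | 0.48 v 0.40 | 0.87 v 0.80 |
| 40 v 80 | 75%, early | 82.1 v 90.7 | 2.49 v 2.95 | 0.60 v 0.40 | 0.93 v 0.80 |
| 40 v 80 | 75% placebo, 25% drug, spread | 85.3 v 92.1 | 2.61 v 2.96 | 0.46 v 0.40 | 0.82 v 0.80 |
| 40 v 80, median onset 56 days | 75%, early | 71.7 v 92.1 | 2.24 v 2.93 | 0.65 v 0.40 | 0.93 v 0.80 |
| 40 v 70 | 10%, spread | 68.1 v 68.7 | 2.27 v 2.27 | 0.41 v 0.40 | 0.71 v 0.70 |
| 40 v 70 | 75%, early | 56.2 v 67.6 | 2.03 v 2.27 | 0.60 v 0.40 | 0.87 v 0.70 |

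Both curves rise in every row. The placebo curve rises clearly more when many failures stop early or when placebo failures stop more often; otherwise the two rises are similar. With no treatment effect and equal stopping, the rejection rate stays at about 4 to 5%.

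**5. Alpha.** The fallback allocations sum to 0.046 + 0.002 + 0.001 + 0.001 = 0.05. TTFSF is tested at 0.05 only if RBANS, mRS and rescue all succeed; its own share is 0.001. At 0.001, with 40% v 80% and 75% stopped early, power is 31.7% v 50.6%.

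**The case against.** **The analysis is no longer planned.** This stands. A reader might infer that the reported TTFSF result will carry a biased hazard ratio or lose power. It will not: SAP Amendment 1 has no log-rank test, hazard ratio or curve for TTFSF.

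**The loss may be negligible.** This also stands as a limit. If the 10% dropout in Section 9.8 were the whole of the stopping, then 0.10/0.60 = 17% of placebo failures would stop, and the loss is about 1 point. A reader might instead infer a large loss: with onset uniform over Days 1 to 141 and half of failures stopped on Days 29 to 57, power is 78% v 92%. That onset has a median near Day 71, against the 28 days the protocol cites. Early stopping is nevertheless plausible, because 7.1.3 ties absence of benefit to the first 4 weeks, and the dropout figure is not described as covering stops for lack of efficacy.

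**Not every stop under 7.1.3 is an informative censoring.** Correct. A recurrence after a first 28-day run comes after the TTFSF event. Stops for mRS or RBANS worsening are not in themselves seizure failures. TTSFM does not state the last-IMP-day rule, so the point does not carry over to it unchanged.

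**The sponsor saw the issue.** The SAP change log (6.8.1) records a TTFSF sensitivity analysis added because of informative censoring from withdrawals. The reduced SAP no longer contains it. Its removal is not an error, but the entry supports the reasoning here.

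**Strategies may differ by endpoint.** They may, but a while-on-treatment label does not justify discarding an observed on-treatment non-event.

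**Conclusion.** The point holds as a flaw in the protocol's TTFSF analysis: the censoring rule contradicts its stated assumption for participants stopped for lack of seizure improvement. In that analysis, both success curves are inflated, the hazard ratio moves toward 1, and power falls by roughly 0 to 20 points at two-sided 5%. The central illustration is about 4 points (40% v 80%, 28-day median onset, half of failures stopped on Days 29 to 57). These sizes rest on assumed stopping fractions, stop days and onset.

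Two stronger readings are not supported. The rule does not inflate only the placebo curve. Nor does it favor the drug: with equal stopping it is conservative.

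What remains live under the SAP is narrower. Section 5.4.4 does not say how participants who never reach 28 seizure-free days enter a continuous summary. Averaging achievers only, or mixing in censoring days, would again leave failures out.

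**What to change.** **Protocol Table 9-5.**
- Treat permanent IMP discontinuation for absence or loss of clinical benefit, or rescue, before any 28-day seizure-free run as a non-event kept at risk to the end of the planned Treatment Period. A competing event with cumulative incidence is an alternative.
- Participants who already had a 28-day run keep their event.
- Censor on the last IMP day only for other reasons.
- Report the current rule as a sensitivity analysis.

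**SAP 5.4.4.** Apply the same rule. Per arm, give the number reaching seizure freedom out of all randomized, and carry non-achievers as not reached by the end of treatment. This replaces a continuous summary of achievers alone or of mixed event and censoring days.

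**Cost.** Wording only. Reasons for discontinuation (SAP 5.2) and for rescue (SAP 5.4.3) are already collected, and the stopping rule is untouched. The estimand changes from while-on-treatment to composite, so some stops driven by mRS or RBANS worsening will count as non-achievement; the retained sensitivity analysis shows how much that matters.

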### 9.3.3 Exploratory efficacy analyses

#### 9.3.3.1 Time to seizure freedom maintenance (TTSFM)

The time to seizure freedom maintenance (TTSFM) defined by the number of days after randomization to the first day of the 28 consecutive days without seizures, ‘maintained until the end of the Treatment Period (Week 25)’.

This analysis and summaries of the time to seizure freedom maintenance endpoint will be performed on the RS utilizing the methodology as described for the TTFSF endpoint (see

Section 9.3.2.4). The participants who do not reach the described endpoint criteria will be censored at the last follow-up timepoint.

In addition, as a further exploratory endpoint, this analysis and summaries will be repeated for only the subgroup of participants who achieved the seizure freedom endpoint criteria.

### 9.3.3.2 Seizure control

Seizure frequencies will be recorded on a daily basis across the 24 weeks of randomized therapy and during a variable Screening Period, based on the specific categories of seizure count (“0-None,” “1-5,” “6-10,” “11-20,” and “More than 20”) that are collected in the myUCB 4me participant seizure app.

For each participant, a median category of seizure counts will be calculated for each week that the participant is in the randomized treatment period, such that each participant has one average median value for that week, along with a minimum and maximum category range. For the Screening Period, a Baseline median category will be calculated for each participant, in the same way as described for each week of randomized treatment. This will be to utilize the screening data collected in the period up to 6 weeks immediately prior to randomisation. All data will then be summarized across time for all participants giving the number of participants falling into each of the median categories across the 24 weeks by randomized treatment arm.

Two success criteria will be considered based on seizure control. ‘Good control’ and ‘Moderate control’; full details will be provided in the SAP.

Any participant who does not reach the end of Week 24 will be considered to have failed both these success criteria. In the case of 7 missing data points over an entire week, this will be imputed from the previous weeks data.

The proportion of participants who achieve ‘Good control’ and ‘Moderate control’ will be summarized and analyzed on the RS. Specifically 2 models will be created to analyze this data, one for each of the success control criterion. A logistic regression model adjusting for the effect of randomized treatment, Baseline median seizure category level, stratification factors and also the use of prior disease modifying treatments, will be used to test for any difference between the randomized treatment arms. The resulting rozanolixizumab versus placebo common OR will be reported. Additionally, the other estimands as described for the primary endpoint in Section 9.3.1.1 will be considered. Full details will be provided in the SAP.

